Re-entry, the period when youth transition from detention facilities back to the community, represents a critical juncture and a high-risk period for re-engaging in substance use. In total, 88,000 detained youth are released annually in the US, most of whom are poor and of color. Within 3 years of release, 75% of adolescents are re-arrested, with highest risk among youth with SUD. Adolescent SUD presence and severity strongly predict re-arrest and less time attending school or being employed. Thus, adolescent SUD not only lead directly to incarceration, but also contribute to low educational attainment and future unemployment, which further increase lifetime incarceration risk and perpetuate individual and intergenerational social disadvantage. Furthermore, the risk of mortality in the first 2 weeks after release for adult former prisoners is 3.5 times that of the general adult population, with the leading cause of death being drug overdose, most commonly cocaine, psychostimulants, and opioids. Formerly incarcerated youth similarly demonstrate high premature mortality. Although many youth express plans to reform and to stay “clean” from drugs upon release from detention, the challenges of returning to chaotic and even dangerous home environments while simultaneously transitioning out of probation schools and correctional health systems—all while confronting the normal developmental tasks of adolescence—make healthy reentry extremely difficult without adequate supports and clinical treatments.

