## **STATISTICAL DESIGN AND POWER**

### **Analytic Strategy**

For each of the aims, we will compare participants who received WPC pre-release services (control group) to participants who received WPC pre-release and post-release services (intervention group). To address possible differential uptake or attrition, we will also conduct treatment received analyses, using the percent time young people participated in the post-release program (9 months total for the initial cohort and 6 months total for the final cohort) as the predictor of outcome. We will also examine for balance on sociodemographic variables and other characteristics of interest between the intervention and control groups as a means of examining for selection bias. To address missing data, in the main analysis, we will use generalized mixed effects model for repeated measures, under the missing-at-random assumption. In addition, using multiple imputations with pattern-mixture models, we will conduct sensitivity analyses to investigate whether our findings are robust to the missing mechanisms (i.e., assuming missing-not-at-random). In particular, we will consider a scenario which is least favorable to the intervention arms; that is, a scenario where the missing observations in the intervention arm follow the same pattern as the one in the control arm.

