#### **Aim 1: Measure the impact of the WPC Reentry intervention targeting recently incarcerated young people on decreasing rates of 30-day use and risky use of marijuana, alcohol, and other drug use.**

*Hypothesis 1:* Young people receiving the WPC intervention will have less substance use at follow-up (3 and 9 months for initial cohort, and 4 and 6 months for final cohort) compared to their in the control group.

For the main outcome, percentage of days used marijuana in the last 30 days, we will conduct a linear mixed effects regression model to account for repeated measurements within individual young people. We will perform unadjusted and adjusted comparisons, controlling for baseline demographic (race/ethnicity, age, parental SES) and substance use characteristics, as well as any variables found to be differential between the intervention and control groups. Similar analyses will be carried out to examine the impact of WPC on percentage days used alcohol and other drugs, and risky use of marijuana, alcohol, and other drugs. We will estimate the treatment effect on marijuana use with the adjustment of incarceration based on the principle stratification analysis.

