### **Sample Size Estimate**

We estimated power for a 2-arm pilot trial. We plan to recruit and consent 160 transition-age young people exiting jail. With a sample size of 160, we believe that our study will be adequately powered to detect a minimal detectable difference in the percentage of days used marijuana in the past 30 days of 17%, which is equivalent to a decrease of 5 days of marijuana use in a 30-day period. This difference is within the observed effect seen in a prior study of marijuana use among reentry young people, which found a range of intervention effects from 11% to 38%. This calculation assumes 10% attrition rate at 3 months, two-sided test with alpha 0.05, and 80% power.

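### The SAP labels a control-based imputation as the least favorable case, but it is only moderately pessimistic and nothing harsher is specified

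*SAP*

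**What the plan says.** The SAP (Analytic Strategy) sets out the main analysis as follows: "we will use generalized mixed effects model for repeated measures, under the missing-at-random assumption". It then turns to data missing not at random, using multiple imputation with pattern-mixture models: "we will conduct sensitivity analyses to investigate whether our findings are robust to the missing mechanisms". One scenario is spelled out, and the SAP describes it as "least favorable to the intervention arms; that is, a scenario where the missing observations in the intervention arm follow the same pattern" as in the control arm. The connecting phrase makes this a definition: control-like outcomes are taken to be the worst case for WPC.

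The protocol and SAP text available for review gives no shift parameter, no tipping point and no scenario in which missing WPC youth do worse than comparable controls. Nor does it name the control-based variant or the covariates in the imputation model.

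Two related plans do not fill the gap. One is in the Analytic Strategy: "To address possible differential uptake or attrition, we will also conduct treatment received analyses". The other is in Aim 1, where the effect on marijuana use is estimated "with the adjustment of incarceration based on the principle stratification analysis". Neither imputes outcomes worse than control.

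On the amount of missing data, the Sample Size Estimate says: "This calculation assumes 10% attrition rate at 3 months". Follow-up is planned at "3 and 9 months for initial cohort, and 4 and 6 months for final cohort". No attrition figure is given for 4, 6 or 9 months.

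**The concern.** Giving missing WPC youth control-like outcomes removes much or all of the benefit among them but adds no harm. Any scenario in which they do worse than comparable controls is less favorable to WPC, so the label is wrong whatever the numbers.

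It matters because the stated purpose is to learn how far findings withstand departures from missing at random. A reader told that a benefit survived the least favorable case would think the hard end of the range had been tried.

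The design gives no reason to treat the control pattern as a floor. Youth opt in to or out of WPC (Protocol, Recruitment and Consent, adult population), and the SAP itself plans a balance check for selection bias. The protocol's Background says: "Adolescent SUD presence and severity strongly predict re-arrest and less time attending school or being employed". Heavier users could therefore also be harder to reach. That last step is our inference, and the documents give it no size.

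**Working it through.** **Inputs.** From the SAP: 160 participants, a detectable difference of 17 percentage points in days of marijuana use, 10% attrition at 3 months, two-sided alpha 0.05, 80% power. From the protocol: 80 per arm. Assumed: equal missing share m in both arms, m of 20% and 30%, an observed benefit of 17 points, and an approximately normal outcome.

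**The plan's own figure.** The SAP gives no SD, so its sample size can only be solved backwards. With 80 × 0.9 = 72 evaluable per arm:

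SD = 17 / [(1.960 + 0.842) × √(2/72)] = 36.4 points.

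This SD is implied, not stated.

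**Shrinkage, balanced arms, no covariates.** At a single time point, or under jump-to-reference, the estimate becomes 17(1−m). Under copy-reference with only the second of two visits missing and visit correlation ρ, it becomes 17[1−m(1−ρ)].

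| Missing share | 17(1−m) | Copy-reference, ρ = 0.6 | Copy-reference, ρ = 0.3 |
|---|---|---|---|
| 10% | 15.3 | 16.3 | 15.8 |
| 20% | 13.6 | 15.6 | 14.6 |
| 30% | 11.9 | 15.0 | 13.4 |

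So (1−m) is the most shrinkage in this setting, and the sign does not change.

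**Shift needed to lose significance, one time point.** If missing WPC youth are δ points worse than controls, the estimate is 17(1−m) − mδ. Holding the standard error at its completer value, SE = 36.4 × √(2/n):

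- 10% missing: n = 72, SE = 6.07, threshold 1.96 × 6.07 = 11.89. Control-based estimate 15.3, p = 0.012. Tipping δ = (15.3 − 11.89)/0.1 = 34 points.
- 20% missing: n = 64, SE = 6.44, threshold 12.61. Control-based estimate 13.6, p = 0.035. Tipping δ = (13.6 − 12.61)/0.2 = 4.9 points, about 1.5 days in 30.
- 30% missing: n = 56, SE = 6.88, threshold 13.49. Control-based estimate 11.9, p = 0.08. The scenario itself already loses significance.

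With Rubin's variance, which grows as the imputed values move away from the observed ones, the tipping shift is about 30 points at 10% and about 5 at 20%. Multiple imputation on constructed data gave about 29 and 4. For SDs from 30 to 42, the shift runs from 46 down to 14 points at 10% missing and from 15 down to 0 at 20%.

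**Imbalanced arms with a covariate.** Suppose imputation conditions on baseline use with slope 0.6, the conditional benefit is 17 points, and WPC baseline use is worse by 26.7 points (10% missing) or 25 points (20% missing). The unadjusted benefit under missing at random is 17 − 0.6 × 26.7 = 1.0, or 17 − 0.6 × 25 = 2.0. Control-based imputation removes m × 17, leaving 1.0 − 1.7 = −0.7 or 2.0 − 3.4 = −1.4. The sign changes, in a deliberately extreme example.

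**False benefit.** Simulated trials had no true overall difference, 80 per arm and SD 36.4. The entries are the proportion showing a significant WPC benefit under the SAP scenario (nominal 2.5%).

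| Missing youth worse by | Arm affected | 10% missing | 20% missing | 30% missing |
|---|---|---|---|---|
| 17 points | WPC only | about 3% | about 4% | about 5% |
| 30 points | WPC only | about 5% | about 10% | about 20% |
| 17 or 30 points | both arms | under 2% | about 1% or less | about 0.5% or less |

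**The case against.** The strongest reply is that the SAP already does much of what is asked. It plans more than one sensitivity analysis, introduces this scenario as a particular case, and states exactly what is assumed, so a careful reader can see what was tested. Controls receive pre-release WPC services, which makes a control-like outcome a natural assumption for WPC youth who disengage after release. This is an exploratory pilot, and at the only attrition figure in the documents the shift needed to overturn a result is large. All of this stands, and it keeps the point small. It does not make the label right, and no further scenario is actually specified.

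Three stronger readings are tempting, and the documents do not support them:

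- A reader might infer that control-based imputation can never bring a favorable estimate to zero or reverse it. That holds for balanced arms without covariates. These arms are self-selected, and the example above shows a small benefit changing sign.
- A reader might infer that the scenario never gives missing WPC youth worse values than the control average. If imputation uses baseline or earlier visits, WPC dropouts with heavy prior use can be imputed above that average. What is missing is a shift beyond controls with the same history.
- A reader might infer that the SAP scenario would produce false findings of benefit. The inflated rates arise only when missing WPC youth are worse and missing controls are not. The protocol's remark on substance use severity concerns youth in general, not one arm. With the same shift in both arms, the scenario is conservative.

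**Conclusion.** The label is wrong as written, and no scenario beyond it is specified. Control-based imputation is a legitimate, moderately pessimistic analysis; the fault lies in calling it the least favorable one and stopping there. The consequence is a possible overstatement of robustness in the report. The primary estimate does not change.

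This is a minor point. At the stated 10% attrition, a 17-point benefit would survive unless missing WPC youth were about 30 to 34 points worse than controls. It would matter more if missingness reached about 20%, where about 4 to 5 points is enough. These figures rest on the back-solved SD, equal missingness by arm, an unadjusted comparison at one time point and approximate normality on a bounded scale. Missing shares above 10% are assumptions, and the documents neither give nor rule them out for the later visits.

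**What to change.** In the Analytic Strategy, replace the wording *least favorable* with *control-based*, and have the authors name the variant (for example jump-to-reference or copy-reference) and the variables in the imputation model.

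Within the pattern-mixture multiple imputation already planned, prespecify a delta-adjusted tipping-point analysis for the main outcome. Worsen missing WPC values in steps from the control-based value toward the scale limit of 100% of days, keeping missing controls at missing at random. Optionally, add a version that also shifts missing controls. Report the shift at which the confidence interval first includes zero, and the missing share by arm and visit, so that readers can judge whether such a shift is plausible.

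The cost is one reworded sentence, a short added specification and a few more imputation runs. Design, data collection and the primary model stay as they are. The downside is that a result may look less robust than under the present plan.

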#### **Aim 1: Measure the impact of the WPC Reentry intervention targeting recently incarcerated young people on decreasing rates of 30-day use and risky use of marijuana, alcohol, and other drug use.**

*Hypothesis 1:* Young people receiving the WPC intervention will have less substance use at follow-up (3 and 9 months for initial cohort, and 4 and 6 months for final cohort) compared to their in the control group.

For the main outcome, percentage of days used marijuana in the last 30 days, we will conduct a linear mixed effects regression model to account for repeated measurements within individual young people. We will perform unadjusted and adjusted comparisons, controlling for baseline demographic (race/ethnicity, age, parental SES) and substance use characteristics, as well as any variables found to be differential between the intervention and control groups. Similar analyses will be carried out to examine the impact of WPC on percentage days used alcohol and other drugs, and risky use of marijuana, alcohol, and other drugs. We will estimate the treatment effect on marijuana use with the adjustment of incarceration based on the principle stratification analysis.

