This study will use an observational survey research design to understand the interrelationships between social networks, substance use, and care utilization for TAY who transition home following incarceration. A mixture of closed-ended surveys along with open-ended focus group discussions will be used. Participants will be asked to complete three surveys (baseline, as well as 3 and 9 months post-release). For TAY exiting jail, baseline surveys will be conducted while detained. For TAY exiting the juvenile justice system, baseline surveys will be conducted in the community, up to one month after their release from incarceration. From the surveys, the research team will identify participants with high and low health service utilization, and invite them to participate in one focus group interview. Participation in the study will take up to 3 hours, which includes survey completion and focus group participation.

Medical records, with limited information, will also be requested from LA Department of Health Services for adults eligible for the Whole Person Care intervention.

Furthermore, we intend to assess the intervention's fidelity by observing youth-WPC coach interactions and inviting at least 5 WPC coaches to participate in surveys and interviews. This will also help assess the coaches' perceptions of successes and challenges with adherence to the WPC protocol. Coaches will be invited to participate in the study through a separate consent process.

Amendment 05/27/20:

In response to COVID-19, we will conduct monthly qualitative interviews with the 19 participants that are currently enrolled in the study. Interviews will be done over the phone until we are permitted to resume in-person procedures. We will also add an additional time point for when we administer the follow-up survey, 1-month post release.

Amendment 10/28/2020:

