****TAY Exiting the Adult Criminal System (ADULT POPULATION)****

Study population:

Participants who are eligible for the Whole Person Care—Los Angeles (WPC-LA) Reentry post-release program will be eligible for the adult population of this study. The WPC Reentry program, implemented by the Los Angeles County Health Services Department, links jail inmates with community-based health, behavioral health, and social service providers as they return to the community. The intervention connects participants to Community Health Workers (CHWs) with a prior personal history of incarceration. CHWs assist participants in engaging with community-based health, behavioral health, and social service providers during reentry to the community. Services provided include mentorship and social support; health and social service navigation; linkage to housing, employment, education, legal assistance and social supports; accompaniment to key health and behavioral health appointments; assistance with adherence to appointments, treatments and medications; and connection to transportation. The mentorship and social support aspects of the intervention will indirectly target the social networks of participants. The WPC intervention is an existing intervention. The WPC intervention enrolls 750 individuals per month across LA County; approximately 12% are transition age youth ages 18-24. Participants are invited to this program while detained by the WPC case manager. Thus, WPC is a voluntary program. The WPC case manager is responsible for determining eligibility for the WPC reentry program and enrollment in the WPC program, not the research staff.

Recruitment and Consent:

We will recruit 160 adults exiting the LA county justice system – 80 who have enrolled in the WPC program and 80 have not. We anticipate enrolling participants over an approximate 9 month window, aiming to recruit about 9 individuals per arm (WPC and non-WPC) each month. This represents approximately 10% of the eligible population each month for each arm.

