Using the quantitative surveys, we will also conduct a social network analysis, which will help determine why the intervention did or did not demonstrate the expected effect. We will measure how social networks function for youth and whether the insertion of a caring adult can create linkages to substance use services and promote healthier social networks. We will use the approach described in Baron and Kenny (1986) to evaluate whether our data are consistent with a model in which social networks mediate the relationship between WPC receipt and substance use. Primary social network measures will include the change in proportion of peers using substances (alcohol, marijuana, other drugs), limited to those whom the subject interacts with at least weekly. We will compare baseline social network characteristics of the intervention and control groups and control for these measures if significant differences are noted. To test whether youth receiving WPC report a lower proportion of peers in their network engaging in substance use, we will conduct a mixed

effects binomial logistic regression model accounting for repeated measurements within students. We will control for baseline demographic characteristics, as well as any variables found to be differential between the intervention and control groups. Furthermore, we will examine the number of non-using supportive adults in their network using a mixed effects binomial logistic regression model. We will also use mixed effects models to investigate whether network structure differs between study arms and whether intervention youth report stronger connections to healthy peers and adults.

After completion of focus groups, we perform inductive thematic analysis to identify emergent themes. Results will be triangulated with the surveys.

Sample size was determined based on power calculations and the feasibility of the budget in the pending grant. We plan to recruit and consent 160 TAY ages 18-24 exiting the adult criminal justice system and 40 TAY ages 16-19 exiting the juvenile justice system.

V. Characteristics of the Study Population

Maximum number of study participants we hope to enroll: 160 adults exiting the LA county justice system and 40 youth exited the juvenile justice system and 10 coaches/CHWs

Inclusion criteria for TAY exiting the adult criminal system:

1. Age 18-24
2. Fluent in English or Spanish
3. No severe cognitive delay

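### The planned models have no term for the community health worker, so the standard error of the WPC effect is too small if study youth share workers and workers differ in effectiveness

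*SAP*

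**What the plan says.** **Delivery.** The protocol's description of the adult study population says: "The intervention connects participants to Community Health Workers (CHWs) with a prior personal history of incarceration". These workers give mentorship, navigation and accompaniment. Under the SAP's Analytic Strategy, controls have pre-release services only and the intervention arm adds the post-release programme. The CHW relationship after release therefore exists in one arm.

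**Correlation structure.** For Aim 1 the SAP states "we will conduct a linear mixed effects regression model to account for repeated measurements within individual young people". Aim 2 (generalized linear mixed models) and the Aim 3 model for substance-using peers likewise account for repeated measurements within the person, as does the protocol's Statistics and Data Analysis section. The principal stratification analysis (Aim 1) and the network-structure models (Aim 3) specify no random effects. Neither the protocol nor the SAP text available mentions a worker term, cluster-robust standard errors, an ICC or a design effect.

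**Sample size.** "We plan to recruit and consent 160 transition-age young people exiting jail"; the protocol splits these into "80 who have enrolled in the WPC program and 80 have not". The detectable difference is 17 percentage points. The SAP adds: "This calculation assumes 10% attrition rate at 3 months, two-sided test with alpha 0.05, and 80% power".

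**Coach numbers.** The Lay Summary plans on "inviting at least 5 WPC coaches to participate in surveys and interviews". The enrolment maximum under Characteristics of the Study Population includes "40 youth exited the juvenile justice system and 10 coaches/CHWs".

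**The concern.** A random effect for the person absorbs the correlation between one youth's own surveys. It cannot absorb correlation between different youth who have the same CHW. Where one worker has several study participants, that worker's skill or style is shared among them, so they carry less information than the same number of independent youth. Controls have no such shared source. This is a partially nested design.

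Variation between workers is not far-fetched. The protocol's fidelity section measures how often and how long youth see their coaches, how youth perceive them, and what difficulty coaches have in adhering to the programme.

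At stake are the width of the confidence interval for the WPC effect, the 5% error rate of its test, and the 80% power claimed for 17 points. As a pilot, the study is also meant to inform a larger grant application, and without worker identity it cannot estimate the between-worker variance that a later trial would need.

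**Working it through.** **Inputs from the documents.** N = 160, 80 per arm; 10% attrition, so 80 × 0.9 = 72 evaluable per arm; two-sided alpha 0.05; power 80%; detectable difference 17 points.

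**Inputs assumed.** The worker ICC (0.05, with 0.10 as a harsher case) and the number of CHWs, J, serving the WPC youth. The documents give neither.

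**The plan's own figure.** No standard deviation is stated, so the 17 points cannot be checked independently. Solving 17 = (1.96 + 0.84) × SD × √(2/72) gives SD ≈ 36.4 points. With that SD, N = 160 follows for independent youth with no design effect.

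**Formula.** With total variance held constant and clustering in the WPC arm only:

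- DE = 1 + k × ICC, where k is the average number of other study youth sharing a participant's CHW
- f = (DE + 1)/2, the variance of the difference relative to independence
- type I error = 2 × [1 − Φ(1.96/√f)]
- detectable difference = 17 × √f

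For equal caseloads, k = 72/J − 1. For youth spread at random over many workers, caseloads are unequal and k = 71/J. Type I error does not depend on the back-solved SD.

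**Worked case, 10 CHWs, ICC 0.05.** k = 7.2 − 1 = 6.2; DE = 1.31; f = 1.155; √f = 1.075. Type I error = 2 × [1 − Φ(1.824)] = 6.8%. Detectable difference = 17 × 1.075 = 18.3 points.

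| CHWs (spread) | k | f at ICC 0.05 | Type I error | Detectable difference | Power at 17 points | Type I error at ICC 0.10 |
|---|---|---|---|---|---|---|
| 5 (equal) | 13.4 | 1.335 | 9.0% | 19.6 | 67.9% | 12.9% |
| 10 (equal) | 6.2 | 1.155 | 6.8% | 18.3 | 74.1% | 8.7% |
| 20 (equal) | 2.6 | 1.065 | 5.8% | 17.5 | 77.5% | 6.5% |
| 45 (random) | 1.58 | 1.039 | 5.5% | 17.3 | 78.5% | 5.9% |
| 68 (random) | 1.04 | 1.026 | 5.3% | 17.2 | 79.0% | 5.6% |

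The two spreads differ little: with 10 CHWs and ICC 0.05, random allocation gives 7.1% instead of 6.8%. A simulation of 20,000 null datasets per setting, with equal caseloads and an ordinary t-test, gave 8.6% (5 CHWs), 7.0% (10) and 5.9% (20) at ICC 0.05, in line with the formula.

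**Where 45 and 68 come from.** The protocol says WPC enrols 750 people a month, and the SAP gives the post-release programme as 6 or 9 months. If all enrollees stayed throughout, 750 × 6 = 4,500 to 750 × 9 = 6,750 would be active at once. An assumed caseload of 100 then needs 45 to 68 CHWs.

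These figures treat the comparison as one time point and use large-sample critical values. With few workers, correct small-sample degrees of freedom would reduce power further.

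**The case against.** The strongest reply is that sharing of workers is an inference. No section gives a caseload, says how many study youth one CHW serves, or says that a youth keeps the same CHW throughout. A reader might take the 5 and 10 coaches as the workforce, divide 80 youth by them, and conclude that 8 to 16 youth share each worker. The documents do not support that. Those are enrolment figures for coach surveys and interviews, and the consent section says that a youth can take part even if his or her coach does not. If ten CHWs carried the whole programme, the full-retention arithmetic would give them 450 to 675 clients each, which points to a larger pool. This objection stands and pulls the likely size towards the lower rows of the table. It is not decisive, since early dropout or workers dedicated to young clients would mean fewer CHWs per study youth.

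A second reply is that, if inference is only to this programme with the workers who served, omitting a random CHW effect is defensible. That is a coherent target, but the plan does not state it, and a pilot for a larger study usually looks beyond the present workers.

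Third, a CHW variance may be poorly estimated here, whether from very few workers or from many workers with one participant each. That stands, and favours a sensitivity analysis over a change to the primary model.

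**Conclusion.** The point holds conditionally. The planned models leave out a source of correlation that the delivery of WPC can create in one arm. With a positive worker ICC and more than one study youth per worker, the standard error is too small; that direction does not depend on the unknown figures.

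The size does. At an assumed ICC of 0.05 it runs from negligible (5.3% to 5.5% with 45 to 68 CHWs) through modest (6.8% with 10) to material (9.0% with 5).

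A reader might infer that the trial's false-positive rate does exceed 5%, or that the 17-point figure is wrong. Neither follows: the documents do not establish that youth share workers or that workers differ, and 17 points is arithmetically consistent with independent youth and an SD of about 36.4.

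In an exploratory observational study whose participants choose whether to enter WPC, selection bias is the larger threat. This is a cheap improvement, not a flaw that invalidates the analysis.

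**What to change.** 1. Add the assigned CHW, as a code, to the youth fidelity form at each follow-up, with a rule fixed in advance for youth who report more than one.
2. Prespecify a sensitivity analysis of the Aim 1 to 3 comparisons with a CHW random intercept in the WPC arm only, or CHW-clustered standard errors, using small-sample degrees of freedom in either case.
3. Report the number of CHWs and the distribution of study youth per CHW, so that readers can see which row of the table applies.

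**Cost.** One data item and one extra model. The form as described does not list worker identity. The October 2020 amendment dropped chart abstraction, and WPC is not told who takes part, so the item would rest on youth report. Intervals may widen. If most CHWs have a single participant, the CHW variance will be poorly estimated and the result will lie close to the planned model, which is itself worth reporting.
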